4.2 Toxicities and Dosing Delays/Dose Modifications

Any patient who receives treatment on this protocol will be evaluable for toxicity. Each patient will be assessed for the development of toxicity according to the Time and Events table (Section 5.5). Toxicity will be assessed according to the NCI Common Toxicity Criteria for Adverse Events (CTCAE), version 5.0. Dose adjustments should be made according to the system showing the greatest degree of toxicity.

Cabozantinib and pembrolizumab have class specific safety profiles based on their mechanism of action but may also cause AEs that overlap. For management of AEs which can be clearly attributed to cabozantinib or pembrolizumab, independent dose modification for either agent is allowed. Examples of VEGFR TKI associated AEs caused by cabozantinib are hypertension and hand-foot syndrome. Examples of immune-related AEs caused by pembrolizumab are pneumonitis and endocrinopathies. For AEs without clear attribution to either study treatment, management of toxicity should include dose modifications of both agents per the discretion of the investigator. Examples of overlapping AEs are diarrhea and transaminase increases.

Protocol #: UCI 18-124 MP 10/11//2022

Dose Modification Table

Dose Level	Agent	Dose
1 (starting dose)	Cabozantinib	40 mg
1 (starting dose)	Pembrolizumab	200 mg
-1 (50% reduction)	Cabozantinib	20 mg
-2	Cabozantinib	20 mg every other day

Toxicities:

Toxicity Dose Reductions			
NCI CTC Grade	Cabozantinib	Pembrolizumab	
Grade 0-2	No change from original starting dose	No change from original starting dose (unless described in 4.2.1)	
Intolerable grade 2 or grade 3	Hold until resolved to < Grade 1 then resume to dose level 1 or -1, depending on physician assessment	Hold until resolved to < Grade 2, then resume at dose level 1 (unless described in 4.2.1)	
Second episode of grade 3 or intolerable grade 2 first episode of grade 4 toxicity	Hold until resolved to ≤ Grade 1 then reduce to dose level one less than previous (i.e1 or -2) Discontinue permanently (unless investigator determines patient is deriving clear clinical benefit)	Discontinue permanently (unless described in 4.2.1)	
Third episode of grade 3	Remove subject from trial	Not applicable	

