4.4 Cabozantinib adjustment for toxicity

The most frequent AEs experienced by ≥ 20% of subjects treated with cabozantinib in descending order of frequency were diarrhea, fatigue, decreased appetite, nausea, weight decreased, PPES, vomiting, constipation, hypertension, dysgeusia, dysphonia, asthenia, and dyspnea.

Subjects may also experience other medically important but less frequent AEs including arterial thrombotic AEs (e.g., deep vein thrombosis [DVT], pulmonary embolism, transient ischemic attack [TIA], and myocardial infarction [MI], severe hemorrhagic events, proteinuria, wound healing complications, gastrointestinal (GI) perforation, abscesses including intra-abdominal and pelvic abscess, GI and non-GI fistula formation, osteonecrosis, and reversible posterior leukoencephalopathy syndrome (RPLS).

Adverse events associated with laboratory abnormalities experienced by ≥ 5% of subjects treated with cabozantinib in descending order of frequency were anemia, AST increased, ALT increased, hypothyroidism, hypokalemia, hypomagnesemia, thrombocytopenia, hypocalcemia, hypophosphatemia, lactate dehydrogenase (LDH) increased, lipase increased, neutropenia, hyponatremia, ALP increased, hyponatremia, and leukopenia.

Many adverse events may occur early (within the first few weeks) in the course of treatment with cabozantinib, as cabozantinib is expected to reach steady state exposure at approximately 2 weeks following first dose. Events that generally have an early onset include hypocalcemia, hypokalemia, thrombocytopenia, hypertension, PPES, abdominal pain, mucosal inflammation, constipation, diarrhea, and vomiting.

Adverse events should be managed with supportive care at the earliest signs of toxicity. Dose reductions and treatment interruptions should be considered. Dose reductions are recommended for events that, if persistent, could become serious or intolerable (Section 4.2).

Cabozantinib should be discontinued for the following AEs: visceral perforation or fistula formation, severe hemorrhage, serious arterial thromboembolic events, nephrotic syndrome, hypertensive emergency, persistent uncontrolled hypertension despite optimal medical management, and reversible posterior leukoencephalopathy syndrome (RPLS).

Gastrocintestinal Disorders

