Gastrointestinal perforation, GI fistula, and intra-abdominal and pelvic abscess: After starting treatment with cabozantinib, subjects should be monitored for early signs of GI perforation such as abdominal pain, nausea, emesis, constipation, and fever especially if known risk factors for developing GI perforation or fistula [37] are present. Discontinue cabozantinib and initiate appropriate management in subjects who have been diagnosed with GI perforation or fistula.

Diarrhea: Subjects should be instructed to notify their physician immediately at the first signs of poorly formed or loose stool or an increased frequency of bowel movements. Guidelines for the evaluation and management of diarrhea are shown in Table 9. Administration of antidiarrheal/antimotility agents is recommended at the first sign of diarrhea as initial management. Some subjects may require concomitant treatment with more than one antidiarrheal agent. When therapy with antidiarrheal agents does not control the diarrhea to tolerable levels, cabozantinib should be temporarily interrupted or dose reduced. When the diarrhea is controlled, retreatment with cabozantinib may be acceptable per investigator decision.

In addition, general supportive measures should be implemented such as continuous oral isotonic hydration, correction of fluid and electrolyte abnormalities, small frequent meals, and stopping lactose-containing products, high-fat meals, and alcohol.

Recurrent or prolonged diarrhea can be associated with anal or perianal skin erosions which increase the risk for anal abscesses, fistulas, or proctitis. Good personal hygiene should be emphasized. Regular examinations of the perianal region should be performed whenever diarrhea has occurred during treatment with cabozantinib. Infections of the perianal region should be treated per local guidelines.

Table 9: Management of Diarrhea Associated with Cabozantinib

Status	Management

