5.6 Removal of Subjects from Study

Patients can be taken off the study treatment and/or study at any time at their own request, or they may be withdrawn at the discretion of the investigator for safety, behavioral or administrative reasons. The reason(s) for discontinuation will be documented and may include:

- 5.5.1 Patient voluntarily withdraws from treatment (follow-up permitted):
- 5.5.2 Patient withdraws consent (termination of treatment and follow-up);
- 5.5.3 Patient is unable to comply with protocol requirements;
- 5.5.4 Subjects who cannot tolerate the minimum protocol-specified dose of study treatment will have study treatment discontinued;
- 5.5.5 Patient demonstrates disease progression or subject no longer experiences clinical benefit as determined by the investigator (unless continued treatment with study drug is deemed appropriate at the discretion of the investigator);
- 5.5.6 Patient experiences toxicity, intercurrent illness, or specific conditions in section 4.2 that makes continuation in the protocol unsafe;
- 5.5.7 Treating physician judges continuation on the study would not be in the patient's best interest;
- 5.5.8 Patient becomes pregnant or patient is breastfeeding (pregnancy to be reported along same timelines as a serious adverse event);
- 5.5.9 Development of second malignancy (except for basal cell carcinoma or squamous cell carcinoma of the skin) that requires treatment, which would interfere with this study;
- 5.5.10 Sexually active subjects who refuse to use medically accepted barrier methods of contraception during the course of the study and for 4 months after discontinuation of study treatment
- 5.5.11 Subjects who cannot tolerate the minimum protocol-specified dose of study treatment will have study treatment discontinued
- 5.5.12 If a subject does not recover from his or her toxicities to tolerable Grade ≤ 2 within 6 weeks, the subject will have study treatment discontinued unless there is unequivocal evidence that the subject is benefitting. In this situation, a subject may be able to restart therapy with a dose reduction of the toxicity and with agreemtn of the investigator
- 5.5.13 Request by regulatory agencies for termination of treatment of an individual subject or all subjects under the protocol

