7.1.2 Special Warnings and Precautions for Use *Cabozantinib*

Dermatologic toxicity: Palmar-plantar erythrodysesthesia syndrome (PPES) was commonly observed in clinical trials; severe PPES (≥ grade 3) also occurred. May require treatment interruption, dosage reduction, and/or discontinuation.

GI toxicity: Diarrhea was commonly observed in cabozantinib-treated patients in clinical trials. May require therapy interruption and/or dosage reduction. Cabozantinib is associated with a moderate emetic potential; antiemetics are recommended to prevent nausea/vomiting. [US Boxed Warning]: Cometriq: Serious GI perforations and fistulas have been reported when used for medullary thyroid cancer; discontinue for GI perforation or fistula formation. May be fatal. Tracheal/esophageal fistulas were also noted; some cases were fatal. GI fistula/perforation (including fatal perforations) were also reported in patients treated with cabozantinib. Monitor for signs/symptoms of perforations and fistulas, including abscess and sepsis. May require therapy discontinuation.

Hemorrhage: [US Boxed Warning]: Cometriq: Serious and occasionally fatal hemorrhage (including hemoptysis and gastrointestinal) has occurred with cabozantinib when used for medullary thyroid cancer. Monitor for signs/symptoms of bleeding and do not administer to patients with severe hemorrhage or a recent history of hemorrhage or hemoptysis. Severe hemorrhage has also been reported in patients with renal cell cancer and hepatocellular carcinoma, including grade 3 or higher events. Do not administer to patients who have a recent history of hemorrhage, including hemoptysis, hematemesis, or melena. Discontinue for grade 3 or 4 hemorrhagic events.

Hypertension: Treatment emergent hypertension was commonly seen in clinical trials (including grade 3 or higher toxicity and hypertensive crisis). Do not initiate cabozantinib in patients with uncontrolled hypertension. Monitor blood pressure prior to therapy initiation and regularly thereafter; withhold for hypertension that is

uncontrolled with appropriate medical management. May require cabozantinib dosage reduction and/or therapy discontinuation.

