Thromboembolic events: Thromboembolic events are frequent in cancer subjects due to procoagulant changes induced by the malignancy or anticancer therapy. DVT and pulmonary embolism have been observed in clinical studies with cabozantinib, including fatal events. Subjects who develop a pulmonary embolism and/or DVT should have study treatment interrupted until therapeutic anticoagulation is established. Treatment with cabozantinib may be resumed in subjects with pulmonary embolism or DVT if it is determined that the event is uncomplicated and that the subject is deriving clinical benefit from cabozantinib treatment and that anticoagulation does not place them at a significant risk that outweighs the benefit of resuming treatment per discretion of the Investigator and according to individual protocols. Therapeutic doses of LMWH or the direct factor Xa oral inhibitors rivaroxaban, edoxaban, or apixaban are allowed for management of thrombotic events. Other oral anticoagulants including coumarin agents (e.g., warfarin), direct thrombin inhibitors (e.g., dabigatran), direct factor Xa inhibitor betrixaban, platelet inhibitors (e.g., clopidogrel), and chronic use of aspirin above low dose levels for cardioprotection per local applicable guidelines are not allowed, until 4 weeks after cabozantinib has been permanently

discontinued. See Section 4.1.2 for additional restrictions on anticoagulation therapy.

Arterial thrombotic events (e.g., TIA, MI) have been observed in studies with cabozantinib. Subjects should be evaluated for pre-existing risk factors for arterial thrombotic events such as diabetes mellitus, hyperlipidemia, hypertension, coronary artery disease, history of tobacco use, and cardiac and/or thromboembolic events that occurred prior to initiation of study treatment. Further treatment with cabozantinib should be discontinued in subjects who develop an acute MI, cerebral infarction, or any other clinically significant arterial thromboembolic complication.

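### The dose table in 4.2 lets cabozantinib resume after a first grade 3 bleed, while 7.1.2 and the 4.4 stop list say to end it, and no order of precedence is stated

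*Combined protocol and SAP*

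**What the plan says.** The dose table in Section 4.2 is organized by CTCAE grade. Its row for intolerable grade 2 or grade 3 toxicity gives this cabozantinib instruction: "Hold until resolved to < Grade 1 then resume to dose level 1 or -1, depending on physician assessment". Level 1 is 40 mg and level -1 is 20 mg. The cell excludes no event type.

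Three other places deal with bleeding on cabozantinib:

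- The stop list in Section 4.4: "Cabozantinib should be discontinued for the following AEs: visceral perforation or fistula formation, severe hemorrhage, serious arterial thromboembolic events", followed by nephrotic syndrome, hypertensive emergency, persistent uncontrolled hypertension and RPLS.
- The Hemorrhage paragraph of Section 4.4, which stops the drug for bleeding that is both serious and life-threatening, or for recent hemoptysis of at least 2.5 mL of red blood.
- The Hemorrhage entry of Section 7.1.2: "Discontinue for grade 3 or 4 hemorrhagic events". The same entry says not to give the drug to patients with a recent history of hemorrhage.

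The Cabozantinib Administration text in Section 1.2 names 4.2 and 4.4 together as the guidelines for reductions and delays. It does not rank them.

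**The concern.** A site usually looks up a grade 3 event in the dose table. For a bleed, the table leads to a hold and a restart at 40 mg or 20 mg, where 7.1.2 ends cabozantinib. A site that follows the table literally could re-expose a patient to a VEGFR inhibitor after a grade 3 hemorrhage.

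The setting makes this more than an editorial matter. Section 4.1.2.1 names gastrointestinal cancers among the settings of increased bleeding risk, and it allows therapeutic LMWH and certain factor Xa inhibitors. Exclusion 3.2.8(i) keeps out patients with significant bleeding in the 12 weeks before first dose. Section 4.6 lists a hold of more than 28 days as a reason to end treatment, so a restart under the table would normally come within about 4 weeks of the hold. On study, the table would then permit dosing at an interval after a bleed that bars entry.

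**Working it through.** The plan states no figure on this point, so the check is a comparison of text, with one piece of arithmetic for context.

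**Step 1. Apply each rule to the same case: a first CTCAE grade 3 hemorrhage.**

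| Source | Threshold stated | Action on cabozantinib |
|---|---|---|
| 4.2 table | Any grade 3 | Hold, then resume at 40 mg or 20 mg |
| 7.1.2, Hemorrhage | Grade 3 or 4 bleed | Discontinue |
| 4.4, stop list | Severe hemorrhage | Discontinue |
| 4.4, Hemorrhage paragraph | Serious and life-threatening bleed, or hemoptysis of at least 2.5 mL | Discontinue; a grade 3 bleed that is not life-threatening is not clearly covered |

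**Step 2. Does the conflict depend on the word severe?** No. Section 7.3.2 equates severe with grade 3, but only on the fallback scale for events without CTCAE grading, so the 4.4 list alone would leave some doubt. Section 7.1.2 names the grade, and that is enough to contradict the table.

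**Step 3. Is the conflict resolved elsewhere?** Section 1.2 cites 4.2 and 4.4 jointly. Section 4.4 refers to 4.2 for dose reductions shortly before its stop list. The cabozantinib column of the table refers to neither 4.4 nor 7.1.2. No sentence says which prevails.

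**Step 4. Does any statistical quantity depend on it?** No. PFS-6 (6.1.6, 9.1) is defined by progression or death. The sample size in 9.2 rests on 5% against 20%. The toxicity boundary counts participants with serious toxicity, and the bleed counts whether or not the drug is restarted.

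**Step 5. Could the case arise in this trial?** Section 7.1.4 lists grade 3 or higher hemorrhage with cabozantinib at 5%. With n patients and rate p, the expected number is n × p and the chance of at least one is 1 − (1 − p)^n.

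- n = 27, p = 0.05: 27 × 0.05 = 1.35; 1 − 0.95^27 = 0.750.
- n = 19, p = 0.05: 19 × 0.05 = 0.95; 1 − 0.95^19 = 0.623.
- n = 27 with an assumed range for p of 0.02 to 0.10: 1 − 0.98^27 = 0.420; 1 − 0.90^27 = 0.942.

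The listed 5% comes without a dose, a tumor type or the share that is grade 3, so it is neither an upper nor a lower bound here. These figures give the chance that the question comes up, not the chance that it is answered wrongly.

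**The case against.** The best defense is that the specific rule governs the general one, and that 4.4 is built this way. For hematologic toxicity, 4.4 says reductions and interruptions are not mandatory, which departs from the table. For grade 3 hand-foot syndrome it requires a reduced dose on restart, where the table also allows the full dose. For electrolyte disorders it sends the reader back to 4.2, so it says so when it wants the table used. For hemorrhage it does not; it says stop. Section 7.1.2 repeats the stop and bars dosing after recent hemorrhage. Entry criteria also lower the risk: besides the 12-week bleeding rule, tumor invading the GI tract and lesions invading major vessels are excluded. This defense carries real weight, and the specific-over-general reading is probably what was intended. What it does not supply is a statement of that order, or a single bleeding threshold within 4.4 itself.

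A reader might infer more than the text supports:

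- *That cabozantinib was meant to have no exceptions, because the pembrolizumab column carries an exception clause.* That clause points to a Section 4.2.1 that does not appear in the text. A stale pointer shows nothing about intent for the other drug.
- *That the removal criteria in 5.6 make the 4.2 table controlling.* The item reads "Patient experiences toxicity, intercurrent illness, or specific conditions in section 4.2 that makes continuation in the protocol unsafe". Toxicity is its own ground there, and the next item allows removal on the physician's judgment.
- *That the table plainly allows continuation after a grade 4 bleed, or repeated restarts.* The entry "Discontinue permanently (unless investigator determines patient is deriving clear clinical benefit" appears to belong to grade 4, but the row layout is broken in the available text. The second-episode instruction, "Hold until resolved to ≤ Grade 1 then reduce to dose level one less than previous", is reached only if the first bleed was wrongly restarted.
- *That perforation, fistula and arterial events are equally unsettled.* Their stop rules are clear: "Discontinue cabozantinib and initiate appropriate management in subjects who have been diagnosed with GI perforation or fistula", and "Further treatment with cabozantinib should be discontinued in subjects who develop an acute MI, cerebral infarction". They are simply further events that the same exception clause would cover.

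**Conclusion.** The inconsistency is real and worth correcting. For a first grade 3 hemorrhage, the cabozantinib column of the 4.2 table permits a restart that 7.1.2 and the 4.4 stop list rule out, and 4.4 carries a second, different bleeding threshold. It is more than a missing detail, because a written rule, followed as it stands, leads to the unsafe action.

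Its size is limited. It concerns patient safety only. At the listed 5% rate, the chance of at least one grade 3 or higher bleed is 75% among 27 patients and 62% among 19. A reader might take these as the chance of an improper restart, but they are not: that would require knowing how often a site would follow the table over the bleeding-specific text, and the documents give no basis for an estimate. The conclusion rests on the explicit grade in 7.1.2 and on the absence of any precedence statement, not on these rates.

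**What to change.** In the cabozantinib column of the 4.2 table, add to the grade 3 and grade 4 rows: *except events for which 4.4 or 7.1.2 requires discontinuation (including any grade 3 or higher hemorrhage): discontinue, do not resume.*

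Use one bleeding threshold in the 4.4 stop list, the 4.4 Hemorrhage paragraph and 7.1.2: *CTCAE grade 3 or higher hemorrhage, or hemoptysis of at least 2.5 mL of red blood.*

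The cost is a wording amendment through the route in 10.7. It adds no visit, procedure or patient. A few patients whose grade 3 bleed has resolved could not resume cabozantinib, but 7.1.2 already requires that.

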4.3 Pembrolizumab adjustment for toxicity

No dosage reductions of pembrolizumab are recommended; treatment is withheld or discontinued to manage toxicities.

Colitis (immune-mediated):

Grade 2 or 3: Withhold pembrolizumab; administer corticosteroids (prednisone 1 to 2 mg/kg/day [or equivalent] followed by a taper); may resume upon recovery to grade 0 or 1 toxicity after corticosteroid taper.

Grade 4: Permanently discontinue pembrolizumab; administer corticosteroids (prednisone 1 to 2 mg/kg/day [or equivalent] followed by a taper).

Dermatologic toxicity (immune-mediated):

Grade 3 severe skin reactions or suspected Stevens-Johnson syndrome (SJS) or toxic epidermal necrolysis (TEN): Withhold pembrolizumab and refer for specialized care for assessment and treatment; may require corticosteroids (based on the severity).

Grade 4 severe skin reactions or confirmed SJS or TEN: Permanently discontinue pembrolizumab and refer for specialized care for assessment and treatment; may require corticosteroids (based on the severity).

Endocrinopathies (immune-mediated):

Grade 3 or 4: Withhold pembrolizumab until clinically stable.

Hyperglycemia, severe: Also administer antihyperglycemics.

Hyperthyroidism, severe (grade 3) or life-threatening (grade 4): Manage with thionamides and beta blockers as appropriate; may resume upon recovery to grade 0 or 1 toxicity or discontinue.

Hypophysitis, grade 2 (symptomatic): Also administer corticosteroids (followed by a taper) and hormone-replacement therapy if appropriate; may resume upon recovery to grade 0 or 1 toxicity or discontinue.

Hypophysitis, grade 3 or 4: Withhold or discontinue pembrolizumab (based on severity); also administer corticosteroids (followed by a taper) and hormone-replacement therapy as clinically indicated.

Nephritis (immune-mediated):

Grade 2: Withhold pembrolizumab; administer corticosteroids (prednisone 1 to 2 mg/kg/day [or equivalent] followed by a taper); may resume upon recovery to grade 0 or 1 toxicity after corticosteroid taper.

Grade 3 or 4: Permanently discontinue pembrolizumab; administer corticosteroids (prednisone 1 to 2 mg/kg/day [or equivalent] followed by a taper).

Pneumonitis (immune-mediated):

Grade 2: Withhold pembrolizumab; administer corticosteroids (prednisone 1 to 2 mg/kg/day [or equivalent] followed by a taper); may resume upon recovery to grade 0 or 1 toxicity after corticosteroid taper.

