Grade 3 or 4 or recurrent grade 2: Permanently discontinue pembrolizumab; administer corticosteroids (prednisone 1 to 2 mg/kg/day [or equivalent] followed by a taper).

Other immune-mediated toxicities:

Grade 2 or grade 3 (based on the severity and type of reaction): Withhold pembrolizumab; may require corticosteroids (based on severity). Upon improvement to grade 0 or 1, initiate corticosteroid taper and continue to taper over at least 1 month. Restart pembrolizumab if the adverse reaction remains at grade 0 or 1 following corticosteroid taper. May consider other systemic immunosuppressants if not controlled by corticosteroids (based on limited data).

Grade 3 (based on the severity and type of reaction) or grade 4: Permanently discontinue pembrolizumab; also administer corticosteroids (may consider other systemic immunosuppressants if not controlled by corticosteroids [based on limited data]).

Recurrent immune-mediated adverse reactions, grades 3 or 4: Permanently discontinue pembrolizumab; also administer corticosteroids (may consider other systemic immunosuppressants if not controlled by corticosteroids [based on limited data]).

Inability to taper corticosteroids: Permanently discontinue pembrolizumab if unable to reduce corticosteroid dose to prednisone <10 mg/day (or equivalent) within 12 weeks after last pembrolizumab dose (may consider other systemic immunosuppressants if not controlled by corticosteroids [based on limited data]).

Persistent grade 2 or 3 adverse reaction (excluding endocrinopathy) that does not recover to grade 0 or 1 within 12 weeks after the last pembrolizumab dose: Permanently discontinue pembrolizumab; also administer corticosteroids (may consider other systemic immunosuppressants if not controlled by corticosteroids [based on limited data]).

Infusion-related reaction:

Grade 1 or 2: Interrupt infusion or slow the infusion rate. Grade 3 or 4: Permanently discontinue pembrolizumab.

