Hepatotoxicity: Immune-mediated hepatitis occurred (grades 2 to 4 hepatitis). The median onset for hepatitis was 1.3 months (range: 8 days to 21.4 months); the median duration was 1.8 months (range: 8 days to over 20 months). Hepatitis

resolved in most patients. Administer corticosteroids (prednisone 0.5 to 1 mg/kg/day [or equivalent] for grade 2 hepatitis, and prednisone 1 to 2 mg/kg/day [or equivalent] forgrade 3 or higher, each followed by a taper), and withhold or discontinue therapy based on the severity of liver enzyme elevations. Systemic corticosteroids were used to manage immune-mediated hepatitis in many patients; the median duration of high-dose corticosteroid therapy was 5 days (range: 1 to 26 days), followed by a taper. Monitor for liver function changes. May require treatment interruption, systemic corticosteroids (for grade 2 or higher toxicity), and/or permanent discontinuation. Pembrolizumab/axitinib combination therapy may result in higher frequencies of grades 3 and 4 ALT and AST elevations (compared to pembrolizumab monotherapy). The median time to onset of ALT elevation was 2.3 months (range: 7 days to ~20 months) for pembrolizumab/axitinib combination therapy, and over half of patients with ALT elevation required systemic corticosteroids; resolution of grades 2 to 4 ALT elevation occurred in most patients. When rechallenged with either pembrolizumab, axitinib, or both, over half of patients did not experience recurrence of ALT elevation to >3 times ULN. Monitor liver enzymes at baseline and then periodically during treatment; consider more frequent liver enzyme monitoring than for pembrolizumab (or axitinib) monotherapy. If liver enzymes are elevated, withhold pembrolizumab and axitinib, and consider corticosteroids as needed.

Hypersensitivity: Hypersensitivity and anaphylaxis have been observed (rare).

Hypophysitis: Immune-mediated hypophysitis occurred (grades 2, 3, and 4). The median time to onset was 3.7 months (range: 1 day to 12 months) and the median duration was 4.7 months (range: 8 days to over 12 months). Most cases were managed with systemic corticosteroids. Nearly half of patients with hypophysitis experienced resolution. Monitor for signs/symptoms of hypophysitis (eg, hypopituitarism, adrenal insufficiency). May require treatment interruption, systemic corticosteroids and hormone replacement therapy (as clinically indicated), and/or permanent discontinuation.

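### The Section 4.2 toxicity table sends pembrolizumab exceptions to a Section 4.2.1 that does not exist, and as written its general rows contradict Section 4.3 in six toxicity-by-grade cells

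*Combined protocol and SAP*

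**What the plan says.** The Toxicity Dose Reductions table in Section 4.2 has a pembrolizumab column with three action cells that carry an exception:

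- Grade 0-2: "No change from original starting dose (unless described in 4.2.1".
- Intolerable grade 2, or grade 3: "Hold until resolved to < Grade 2, then resume at dose level 1 (unless described in 4.2.1".
- The next row, which covers a second episode of grade 3 or intolerable grade 2 and, as the text reads, a first grade 4: "Discontinue permanently (unless described in 4.2.1".

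The heading that follows the table is "4.3 Pembrolizumab adjustment for toxicity". That section gives rules by event. Under colitis it says "Grade 2 or 3: Withhold pembrolizumab; administer corticosteroids". It also withholds at grade 2 for nephritis and for pneumonitis. For pneumonitis it adds "Grade 3 or 4 or recurrent grade 2: Permanently discontinue pembrolizumab", and it has the same permanent stop at grade 3 or 4 for nephritis and for infusion-related reactions. Section 7.1.2 repeats the permanent stop for grade 3 or 4 infusion-related reactions.

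**The concern.** The table is written to yield to event-specific rules, but the section it names is not in the protocol. Nothing in the table points to 4.3, and no sentence ranks the two sections. A site that applies the table literally finds no exception and follows the general row. In some cells that row gives a different action from 4.3, and at grade 3 the difference is between resuming pembrolizumab and stopping it permanently.

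Patient safety is at stake first: the events include pneumonitis, for which Section 7.1.2 reports fatal cases. The second issue is conduct. A patient managed exactly as one section says has been managed against the other, so the violation and deviation definitions in Section 7.3.1 have no single standard to apply. Sections 5.2 and 10.3 provide for participating sites, so a shared understanding within one team cannot be assumed.

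**Working it through.** No arithmetic is involved. The check compares the two sections cell by cell.

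**Step 1: does the target exist?** The text runs from the 4.2 table to the 4.3 heading, and there is no 4.2.1 anywhere else. The pages removed before review do not explain the gap, because the text around 4.2 and 4.3 is continuous. Where other sections send the reader to dose-modification rules, they name 4.2 (Section 5.6 on removal, Section 4.4 on electrolytes) or 4.2 and 4.4 (Section 1.2). None names 4.3.

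**Step 2: compare the cells.** The four toxicities are those with a 4.3 entry that can be set directly against the grade 2 and grade 3 rows. Grade 2 is taken as tolerable, since the table moves intolerable grade 2 to the hold row. Grade 3 is taken as a first episode.

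| Toxicity, grade | 4.2 general row | 4.3 | Conflict |
|---|---|---|---|
| Pneumonitis, 2 | No change | Withhold | Yes |
| Pneumonitis, 3 | Hold, then resume | Stop permanently | Yes |
| Nephritis, 2 | No change | Withhold | Yes |
| Nephritis, 3 | Hold, then resume | Stop permanently | Yes |
| Colitis, 2 | No change | Withhold | Yes |
| Colitis, 3 | Hold, then resume | Withhold, may resume at grade 0 or 1 after steroid taper | No direct conflict |
| Infusion reaction, 2 | No change | Interrupt or slow the infusion only | No direct conflict |
| Infusion reaction, 3 | Hold, then resume | Stop permanently | Yes |

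The count is 2 + 2 + 1 + 1 = 6 of 8, with at least one conflict for each toxicity. The pneumonitis line in 4.3 also stops pembrolizumab for recurrent grade 2; I count that within the grade 2 pneumonitis cell.

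**Step 3: does another section settle it?** For grade 3 infusion reactions 7.1.2 agrees with 4.3, so the table stands alone. For pneumonitis, nephritis and colitis, 7.1.2 says interruption or permanent discontinuation may be needed but ties neither to a grade, so it does not resolve those cells.

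**Step 4: grade 4 endocrinopathy.** The last of the three table cells says to discontinue permanently, while 4.3 says "Grade 3 or 4: Withhold pembrolizumab until clinically stable". This may be a seventh conflict, but I do not count it. The row label runs two conditions together and has two cabozantinib actions against one pembrolizumab action, so two rows may have been merged when the PDF was read. Section 4.3 also allows discontinuation for grade 4 hyperthyroidism and for grade 3 or 4 hypophysitis. The source table should be checked.

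**The case against.** The strongest reply is that this is only a broken cross-reference. Every conflicting cell carries an exception clause, so the general rows give way by their own terms, and the event-specific rules follow immediately under a heading that names pembrolizumab toxicity. The differences listed above are what such exceptions would look like. Numbering slips occur elsewhere: Section 5.1.14 cites 3.1.8.1 for a definition found at 3.1.9.1, and the items under 5.6 are numbered 5.5.x. This stands as an account of the cause: exceptions were intended, and 4.3 is probably where they are. It does not remove the defect, because the reader has to guess both the target and the precedence, and a wrong guess reverses the action at grade 3.

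The grade 2 conflicts also narrow if an event is judged intolerable, because the table then says hold. That is correct, but 4.3 does not make withholding depend on tolerability.

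A reader might infer more than the documents support:

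- **Conflict in every cell.** Two of the eight cells do not directly conflict.
- **An expected number of affected patients, from the Section 7.1.4 rates.** For pneumonitis, colitis and infusion reactions those rates have no grade split, and nephritis appears only in the below-1% or case-report group. The conflicts arise at particular grades, so the rates give no usable count.
- **An effect on the six-month progression-free result.** Section 6.1.6 counts progression or death; stopping pembrolizumab is not an event. The documents show no such effect.
- **A missing hepatitis rule that would be needed often.** Section 7.1.2 does leave the choice open ("withhold or discontinue therapy based on the severity of liver enzyme elevations"), but the 4.3 entry for other immune-mediated toxicities covers hepatitis, and 4.4 gives cabozantinib criteria for raised transaminases. The any-grade transaminase rates are not hepatitis rates. A separate hepatitis entry would be new clinical content, not the repair of a contradiction.

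**Conclusion.** The point holds in this form. Three pembrolizumab cells in the 4.2 table refer to a section that does not exist, no text says which section governs, and the general rows as written contradict 4.3 in six of eight cells. Three are no change against withhold (tolerable grade 2 pneumonitis, nephritis and colitis). Three are hold then resume against permanent discontinuation (first grade 3 pneumonitis, nephritis and infusion-related reaction).

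This is operative treatment text, so it is more than a clerical slip. The finding assumes that the table is applied literally and that grade 2 events are tolerable. How many patients would be affected is unknown. The sample size, error rates and decision rule are untouched. Which clinical action is right in each cell is outside this review; the passages must be reconciled.

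**What to change.** 1. In the pembrolizumab column of the 4.2 table, correct the three references to 4.2.1 so that they name the section holding the event-specific pembrolizumab rules, apparently 4.3.
2. Add one sentence stating whether the general row or the event-specific rule governs when they differ.
3. Reconcile the six cells, with the clinical lead choosing each action.
4. Check the source table for the row that includes a first grade 4 event, and reconcile it with the endocrinopathy entry in 4.3 if the conflict is real.

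The clinical lead may also wish to clarify the two lines under other immune-mediated toxicities in 4.3. Grade 3 appears in both the withhold line and the permanent-stop line, each qualified by severity and type of reaction, and 7.1.2 describes when a grade 3 event leads to permanent discontinuation.

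The cost is a short amendment to one table plus one sentence, and edits to 4.3 only where the reconciliation calls for them. It adds no patients, visits or procedures.
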